Once assigned treatment, subjects will take their assigned dose of study medication once a day. Subjects will be asked to return to the clinic every month after randomization until Visit 5 (Month 3) and then quarterly until Visit 8 (Month 12) or receive home care services in lieu of in-person visits (Section 3.6) to undergo study assessments. On Month 12, subjects will take their final dose of study medication and complete the end of study (EOS) assessments. Upon completion of Visit 8 (Month 12), subjects will have the option to enroll in Study PTC518-CNS-004-HD, a Phase 2 long-term extension study, to receive PTC518.

[figure not shown]
For subjects not enrolling in Study PTC518-CNS-004-HD, Visit 8 will be considered the End of Treatment visit, and there will be a Follow-Up Safety Visit on Month 13 via telephone/telehealth to collect adverse events (AEs) and an additional Follow-Up Safety Visit on Month 16 (ie, approximately 4 months after the last dose of study drug) to collect AEs [REDACTED]

[REDACTED]. A final Follow-Up Safety Visit will occur on Month 18 via telephone/telehealth to collect adverse event data.

The safety profile will be characterized via the assessment of treatment-emergent adverse events (TEAEs) and serious TEAEs, laboratory abnormalities, neurofilament light chain (NFL) levels in plasma and cerebrospinal fluid (CSF), and vital signs, the Columbia Suicide Severity Rating Scale (C-SSRS), electrocardiogram (ECG), [REDACTED], and physical examination.

[figure not shown]
The primary efficacy assessment includes blood collection for tHTT protein at Month 3. Secondary efficacy assessments include volumetric magnetic resonance imaging (vMRI) for change in caudate volume (key secondary); other secondary efficacy assessments include blood and CSF collection for mHTT protein at Month 12, and cUHDRS scores. Exploratory assessments will include blood and CSF collection for mHTT protein at Month 3, clinical scales (UHDRS sub-scores [with the exception of the behavioral examination], PBA-s [substituting for the behavioral examination], and Functional Rating Scale [FuRST] 2.0); assessment of gait, balance, and postural sway via Opal wearable devices; plasma and CSF NFL; [REDACTED]; and blood *HTT* mRNA. A complete Schedule of Assessments can be found in [Table 4](#) and the study design is pictured in [Figure 1](#).

Figure 1: Study Design

Abbreviations: ET, Early Termination

Figure 2: Randomization Schema

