3.7. Unscheduled Visits

Unscheduled visits are permitted at the investigator's discretion.

At minimum, adverse events and concomitant medications data must be collected at all unscheduled visits. Unscheduled visits may also include any of the following assessments, at the investigator's discretion:

- Physical examination
- Body weight
- Vital signs
- Pregnancy test
- Dispense study drug (if applicable)
- Drug accountability
- ECG

[REDACTED]

- Blood HTT protein
- Plasma NfL

- Clinical laboratory assessments
- UHDRS Part II (SDMT only)
- UHDRS Part V
- UHDRS Part VI

[REDACTED]

- C-SSRS

In addition, if a subject is intended to enroll in the Phase 2 long-term extension study (Study PTC518-CNS-004-HD), but that study is not yet locally approved by regulatory and/or ethics authorities, the subject may continue within this study attending unscheduled visits approximately every 3 months prior to the end of study visit in order to ensure study treatment is not interrupted and to continue to assess safety parameters. Upon local approval of the Phase 2 long-term extension study (PTC518-CNS-004-HD), the subject will return for the End of Study Visit and will transition into the long-term extension study.

Table 4: Study Design and Schedule of Assessments

	Screening	Baseline		Treatment Period						Safety Follow-Up			Notes	
		Month -57 to -8	Days -22 to -1	Day 1	Month 1	Month 2	Month 3	Month 6	Month 9	Month 12 /EOS/ EOT /ET	Month 13	Month 16	Month 18	
Study Month														The Safety Follow-up visits must be performed for all subjects following either the EOT or ET visit.
Visit	1	2		3	4	5	6	7	8	9	10	11		
Window (days)				±7	±7	±7	±7	±7	±7	±7	±7	±7		
Informed consent	X													
Inclusion/Exclusion	X	X	X											
Medical history	X													
Physical examination	X						X	X	X	X				A complete physical exam will be performed at Visit 1 (Screening) and Visit 8/ET. A brief physical examination, including a neurological examination, will occur at all other timepoints.
Demographics	X													
Concomitant medications	X	X	X	X	X	X	X	X	X	X	X			
Body weight and height		X		X	X	X	X	X	X					Height will be collected at Baseline only.
Vital signs	X		X	X	X	X	X	X	X	X				

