5.3. Secondary Endpoints Analysis

Key Secondary Endpoint Analysis

The percent change from baseline in caudate volume as assessed via vMRI at Month 12 is the key secondary endpoint.

A MMRM model will be used to compare each PTC518 dose group with placebo group for the percent change from baseline in caudate volume as assessed via vMRI at Month 12. The response variable is the percent change from baseline in caudate volume. The model will include fixed effects for treatment, disease stage (by PINHD bin for Stage 2 only and by TFC for Mild Stage 3 only) with baseline caudate volume as a covariate. The time and time by treatment interactions will be included in the model where time is defined as: date of caudate assessment – date of randomization + 1. The intercept and time of collection will be included as a random effect nested within subjects.

The unstructured covariance matrix will be used in the model. If the model does not converge under the unstructured covariance matrix, the Variance Component covariance matrix will be used/. If the model still does not converge, the random effect will be excluded. The treatment effect and treatment difference will be estimated by the LS means and the difference in LS means, along with their SE and with 95% CIs, and the nominal p-values (2-sided) for each pairwise comparison (PTC518 vs. placebo) will be provided.

The caudate volume (left, right, and total [left + right]) and percent change from baseline will be summarized descriptively by treatment group for each visit.

Other Secondary Endpoints Analysis

Other secondary endpoints include:

- Change from baseline in cUHDRS scores at Month 12

An ANCOVA model will be performed to compare each dose group with placebo group for the change from baseline in cUHDRS at Month 12. The model will include treatment group as the independent variable and baseline cUHDRS, disease stage, CAG, age, CAG by age interaction as covariates. The treatment effect and treatment difference will be estimated by the LS means and the difference in LS means, along with their SE and with 95% CIs, and the nominal p-values (2-sided) for each pairwise comparison (PTC518 vs. placebo) will be provided.

- Change from baseline in blood tHTT protein at Month 12

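### Protocol 3.7 does not require the Visit 8 efficacy assessments at Month 12 for subjects awaiting the extension, and the open-ended SAP window would analyse a late Visit 8, above all its cUHDRS score, as Month 12

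*Protocol*

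**What the plan says.** Protocol 3.7 covers subjects who intend to enter the long-term extension before it has been approved where they live. For them, "the subject may continue within this study attending unscheduled visits approximately every 3 months prior to the end of study visit". The stated purposes are to avoid a break in treatment and to keep assessing safety. Once approval arrives, "the subject will return for the End of Study Visit and will transition into the long-term extension study". No limit is set on the wait.

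The mandatory content of such a visit is small: "At minimum, adverse events and concomitant medications data must be collected at all unscheduled visits". The rest is at the investigator's discretion, from a list that includes "Blood HTT protein", UHDRS Parts V and VI, and a cognitive entry that begins "UHDRS Part II (SDMT only". The legible entries do not include vMRI, CSF collection, UHDRS Part I (which gives the Total Motor Score) or Stroop. Two entries are redacted.

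Table 4 has a single column headed "Month 12 /EOS/ EOT /ET". This is Visit 8, with a ±7-day window; vMRI and CSF may be done up to 8 days before it. Protocol 1.2 states: "On Month 12, subjects will take their final dose of study medication and complete the end of study (EOS) assessments".

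SAP Section 1 equates Visit 8 with 12 months of treatment and places the double-blind database lock after it. SAP Table 2 (Section 3.4.6) runs the Month 12 window from Day 331 to 30 days after the last dose. Within a window it ranks the scheduled visit above the assessment nearest the target day. For cUHDRS, SAP 5.3 says: "An ANCOVA model will be performed to compare each dose group with placebo group for the change from baseline in cUHDRS at Month 12".

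**The concern.** A site that reads Section 3.7 beside Table 4 could reasonably postpone Visit 8 until the extension is approved, because the protocol gives Month 12 and End of Study the same column and provides no later End of Study column. Nothing requires the Visit 8 efficacy set to be completed before the waiting period starts.

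All five secondary endpoints are defined at Month 12. Three of them (caudate volume, cUHDRS and CSF mHTT) depend on assessments that are absent from the legible unscheduled-visit list. In a progressive disease a later clinical score carries more decline, and the SAP rules would label it Month 12 without comment. Approval is local, so delays would probably cluster by country, while SAP 3.4.5 pools all centres without adjustment.

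**Working it through.** The plan gives no figure for the number of waiting subjects or for the length of the wait. The check therefore compares the passages and does simple day arithmetic.

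**1. Is Visit 8 fixed at Month 12?** Protocol 1.2 and Table 4 say yes. Section 3.7 puts the End of Study Visit, which is the same Table 4 column, after a wait of open length on continued treatment. Both cannot hold for a waiting subject unless Month 12 and End of Study are two separate visits, and no text says that they are.

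**2. What is lost if Visit 8 is deferred?**

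| Month 12 endpoint | Post-baseline collection (Table 4) | Legible 3.7 list | Model (SAP 5.3) |
|---|---|---|---|
| cUHDRS | Total Motor Score at Months 3, 6, 9, 12; Stroop at Month 12 only | TFC and SDMT only | ANCOVA, no time term |
| CSF mHTT | Months 3, 6, 9, 12 | No | MMRM by visit; earlier visits contribute |
| Caudate volume | Months 3, 12 | No | Actual assessment date, time-by-treatment, random intercept and time |
| Blood tHTT and mHTT | Months 1, 2, 3, 6, 9, 12 | Yes, optional | MMRM by visit |

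cUHDRS needs TFC, Total Motor Score, SDMT and Stroop word reading (SAP 3.4.4). After Baseline it can therefore be calculated only at Visit 8.

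**3. Would the SAP accept a late Visit 8?** The SAP target is Day 360, and ±7 days ends at Day 367. Waits of one or two 3-month intervals (90 or 180 days) give:
- 360 + 90 = Day 450, which is 450 − 367 = 83 days past the visit window
- 360 + 180 = Day 540, which is 540 − 367 = 173 days past it

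If dosing continues to that visit, the Month 12 window reaches Day 450 + 30 = 480 or Day 540 + 30 = 570, so both visits fall inside it. As the scheduled visit, each also outranks an unscheduled sample taken nearer Day 360. SAP Section 1 points the other way: it counts assessments up to 30 days after 12 months of treatment (360 + 30 = Day 390) as double-blind data and only lists later data.

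**4. Size for cUHDRS.** Assume linear change over time. The value at the late visit, relative to the 12-month change, is:
- 450/360 = 1.25
- 540/360 = 1.5

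The overstatement of the mean change is (share deferred) × (delay/360). The share is not stated. For an assumed 5% to 30%:
- 3-month delay: 0.05 × 90/360 = 1.25% to 0.30 × 90/360 = 7.5%
- 6-month delay: 0.05 × 180/360 = 2.5% to 0.30 × 180/360 = 15%

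**The case against.** The strongest reply is that no text tells anyone to omit Month 12. The synopsis and Protocol 1.2 have subjects attend quarterly until Visit 8 (Month 12) and offer the extension after that visit. Table 4 gives the visit a ±7-day window, and SAP Section 1 assumes that Visit 8 means 12 months for everyone. The shared column also covers Early Termination, which need not fall at Month 12, so sharing a column may show only shared assessments. On this reading a completed Month 12 visit comes first, and a later End of Study visit follows the wait. The SAP order would then select the Month 12 assessment correctly.

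This reading is available and may be what was intended. It does not close the point, because Section 3.7 never states it and sites could act differently. It also leaves the final dose at Month 12 in conflict with continued treatment.

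The objection also limits the effect by endpoint, and that stands. The caudate model uses the actual scan date, so the 1.25 and 1.5 ratios do not carry over to it. CSF mHTT has earlier visits in an MMRM, and SAP 5.3 itself expects no large shift months after steady-state exposure, so the linear-decline ratios do not apply there either. Blood HTT can be drawn while waiting. Nothing in the documents suggests that delay would differ by arm under blinded randomization, so no spurious treatment effect is implied. The harm is a Month 12 estimate that mixes follow-up times, with added variation. Finally, two redacted entries mean that the omissions are established for the legible list only.

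**Conclusion.** The point holds as a gap and an inconsistency that need reconciling. As written, the plan permits Visit 8 to be deferred without limit for waiting subjects, and the SAP would analyse the late values as Month 12. cUHDRS is materially exposed, CSF mHTT less so; caudate volume is partly protected by actual time in the model, and blood HTT has an optional fallback. The primary endpoint, at Month 3, is untouched.

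A reader might infer that waiting subjects skip Month 12 and that their secondary endpoints are simply not measured then. The documents do not say so. A reader might also infer that no SAP window could repair the problem. That would be true only for a subject whose Month 12 assessments were in fact not done; where they were done, a bounded window settles the matter.

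The 1.25 and 1.5 ratios per affected cUHDRS score rest on assumed linear decline and delays of 3 or 6 months. The 1.25% to 15% range for the mean also rests on an assumed 5% to 30% deferred. The true share cannot be derived from the documents.

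**What to change.** Reconcile Protocol 1.2, Protocol 3.7 with Table 4, SAP Section 1 and SAP Table 2.

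- **Protocol 3.7 and Table 4.** State that the Visit 8 efficacy set (vMRI, CSF, the UHDRS parts as scheduled including Stroop, PBA-s and blood HTT) is collected at Month 12 within the existing windows (±7 days; vMRI and CSF up to 8 days before), whether or not the subject is waiting for the extension. State that a later End of Study or transition visit does not replace it.
- **SAP Table 2.** Put a fixed upper day on the Month 12 window. Day 390 would match the 30 days allowed after target at Months 6 and 9 and the limit in SAP Section 1. Within this window, use the assessment closest to Day 360.
- **Reporting and sensitivity.** Report how many Visit 8s fell late. Repeat the Month 12 analyses with late values included; for cUHDRS, add actual assessment time as a covariate.
- **Treatment statements.** The sponsor must reconcile the final dose at Month 12 with continued treatment under Section 3.7. This review takes no position on which is right.

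The cost is one clarifying amendment or site letter and a short SAP revision. The downside is that a few late values become missing in the main analysis. For cUHDRS such a subject drops out of the ANCOVA altogether, since there is no earlier post-baseline score. If some Visit 8s have already been deferred (the SAP is dated 17 March 2025), the protocol change cannot recover them, but the window limit, the count and the sensitivity analysis can still be specified before unblinding.

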Clinical laboratory assessments	X	X		X	X	X	X	X	X					Safety laboratory assessments at Baseline should be performed fasted. All other safety laboratory assessments are not required to be performed fasted. Serology performed at Screening only.
CSF collection		X				X	X	X	X					It is recommended that CSF collection be done at least 3 days prior to Day 1. Sample collection may be done up to 8 days prior to Visits 5 through 8. CSF collection must be performed predose.
UHDRS Part I (Motor Assessment)	X		X			X	X	X	X					
UHDRS Part II (Cognitive Assessment)	X (SDMT only)		X	X (SDMT only)	X (SDMT only)	X (SDMT only)	X (SDMT only)	X (SDMT only)	X					At Screening, only SDMT is required to confirm eligibility. Only SDMT is done at Visits 3, 4, 5, 6, and 7.
UHDRS Part IV (Functional Assessment)	X		X			X	X	X	X					

	Screening	Baseline		Treatment Period						Safety Follow-Up			Notes	
		Days -57 to -8	Days -22 to -1	Day 1	Month 1	Month 2	Month 3	Month 6	Month 9	Month 12 /EOS/ EOT /ET	Month 13	Month 16	Month 18	
Study Month														The Safety Follow-up visits must be performed for all subjects following either the EOT or ET visit.
Visit	1	2		3	4	5	6	7	8	9	10	11		
Window (days)				±7	±7	±7	±7	±7	±7	±7	±7	±7		
UHDRS Part V (Independence Scale)	X		X			X	X	X	X					
UHDRS Part VI (Functional Capacity)	X		X			X	X	X	X					
UHDRS Part VII (Clinical Summary)			X			X	X	X	X					
UHDRS Part VIII (Clinical Disposition)			X			X	X	X	X					
PIN _{HD} Calculation	X													TMS and SDMT will be performed at this visit to calculate PIN _{HD} . Only subjects who qualify for enrollment into the Stage 2 group will have PIN _{HD} calculated.
PBA-s			X						X					The PBA-s will be used instead of Part III of the UHDRS.
Timed Up and Go (TUG), 2-minute walk test, and postural sway test			X			X	X	X	X					The Opal wearable device will be worn during these assessments. Each test will be conducted twice: once with a concurrent cognitive interference task and once without.
FuRST 2.0			X			X	X	X	X					
vMRI			X			X			X					Imaging can be done up to 8 days prior to all vMRI visits after Screening.

	Screening	Baseline		Treatment Period						Safety Follow-Up			Notes
		Days -57 to -8	Days -22 to -1	Month 1	Month 2	Month 3	Month 6	Month 9	Month 12 /EOS/ EOT /ET	Month 13	Month 16	Month 18	
Study Month													The Safety Follow-up visits must be performed for all subjects following either the EOT or ET visit.
Visit	1	2		3	4	5	6	7	8	9	10	11	
Window (days)				±7	±7	±7	±7	±7	±7	±7	±7	±7	

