8.1.4. Physical Examination

A complete physical examination will be performed at the timepoints specified in the Schedule of Assessments ([Table 4](#)). A complete physical examination includes general appearance, head, eyes, ears, nose, mouth, throat, thyroid, chest and lungs, abdomen, extremities, neuromuscular system, skin, and lymph nodes.

8.1.6. *Electrocardiogram*

Subjects will be in a supine position for approximately 5 minutes prior to ECG measurements. Measurements will be taken at the times indicated in the Schedule of Assessments ([Table 4](#)) and will be classified as normal/abnormal. In case of a classification as “abnormal,” the abnormality will be described and its relevance in terms of clinical significance documented. The ECGs will be performed in triplicate.

8.1.8. *Laboratory Assessments*

A summary of clinical laboratory tests to be performed is presented in [Table 5](#), with the timing of assessments as indicated in the Schedule of Assessments ([Table 4](#)). Clinically significant laboratory abnormalities which require clinical intervention or further investigation must be reported by the investigator as an AE or SAE as appropriate (Section [8.2.3](#)).

Safety blood samples will be taken under fasted conditions at Baseline. All other safety laboratory assessments are not required to be taken under fasted conditions. As a rule, the blood samples will be taken from the subject by puncture of a vein in the cubital or the antebrachial region. The samples will be sent to a central laboratory in accordance with specifications.

8.1.9. *Neurofilament Light Chain Levels*

The levels of NfL, a biomarker of neuronal injury, will be assessed in plasma and CSF as indicated in [Table 4](#).

Table 5: Summary of Clinical Laboratory Tests

Hematology	Chemistry	Urinalysis ^a	Others	CSF
Hemoglobin	Urea	Urobilinogen	Pregnancy test ^c	NfL
Hematocrit	Creatinine	Nitrite	FSH ^d	WBC ^e
RBC count	Glucose	pH	Serology (HIV, hepatitis B and hepatitis C) ^a	RBC ^e
Platelet count	Sodium	Glucose	Coagulation (PT [sec], PT [INR], aPTT)	Protein ^e
Mean corpuscular volume	Potassium	Albumin	Urine drug screen ^a	Glucose ^e
Mean corpuscular hemoglobin	ALT	Erythrocytes	Plasma NfL	
WBC count	AST	Leukocytes		
WBC differential	GGT	Ketones		
Neutrophils	Bilirubin (total, direct and indirect)	Microscopy ^b		
Band neutrophils	ALP	Specific gravity		
Eosinophils	Albumin	Bilirubin		
Monocytes	Cholesterol (total)			
Basophils	LDL			
Lymphocytes	HDL			
	Triglycerides			

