9.3.2. Safety Analyses

The safety analysis will be performed for the Safety Population. Descriptive statistics of safety will be presented using National Cancer Institute (NCI) CTCAE by treatment group. All TEAEs will be tabulated by System Organ Class and MedDRA Preferred Term. On-study laboratory abnormalities including hematology and chemistry will be summarized using worst grade per NCI CTCAE criteria.

9.3.2.1. *Adverse Events*

AEs will be tabulated using the MedDRA classification system. The frequency of subjects experiencing a specific AE will be tabulated by treatment group, System Organ Class, Preferred Term, seriousness (nonserious versus serious), worst severity, outcome, and relationship to study drug. Subject with AEs leading to death or to discontinuation from treatment, and SAEs will be listed.

9.3.2.2. *Laboratory Abnormalities*

The severity of laboratory abnormalities will be graded using the CTCAE whenever possible. The frequency of subjects experiencing a specific laboratory abnormality will be tabulated by treatment group and worst severity. In addition, the number and percentage of subjects experiencing a specific laboratory abnormality will be tabulated similarly.

9.3.2.3. *Other Safety Assessments*

The results of vital sign measurements, body weight assessments, and ECG assessments will be summarized by treatment group by using appropriate descriptive statistics.

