3.4.2. Baseline Definitions and Change from Baseline

For all efficacy and PD endpoints, unless otherwise specified, the assessments collected at the randomization date will serve as the baseline value. If the randomization visit value is not available, then the last non-missing assessment collected prior to randomization will serve as the baseline. For safety endpoints, the baseline value is defined as the last non-missing assessment prior to the first study drug administration.

For the analysis purposes, change from baseline and percent change from baseline will be derived as follows:

$$\text{Change from baseline} = \text{Post-baseline value} - \text{Baseline value}$$

$$\text{Percent change from baseline} = 100 \times (\text{Post-baseline value} - \text{Baseline value}) / \text{Baseline value}$$

For the vMRI assessments, where the change is directly measured using the Boundary Shift Integral (BSI) for multiple brain areas, the change will not be calculated. For more details, please refer to Section [3.4.3](#).

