6.2. Laboratory Values

Blood samples for hematology, clinical chemistry, and urinalysis will be collected at the visits defined in protocol and the test results will be presented in standard units. The continuous test results and change from baseline will be descriptively summarized by visit and treatment group. Laboratory parameters that will be assessed will include:

- Hematology: hemoglobin, hematocrit, red blood cell count (RBC), platelet count, white blood cell count (WBC), WBC differential, neutrophils, eosinophils, monocytes, basophils, and lymphocytes
- Clinical chemistry: albumin, alkaline phosphatase, alanine aminotransferase, aspartate aminotransferase, bicarbonate, total bilirubin, direct bilirubin, indirect bilirubin, calcium, chloride, total cholesterol, creatinine, gamma-glutamyl transpeptidase, glucose, high-density lipoprotein, low-density lipoprotein, lactate dehydrogenase, potassium, sodium, total protein, triglycerides, urea, and uric acid
- Urinalysis: albumin, bilirubin, erythrocytes, glucose, ketones, leukocyte, microscopy, nitrite, pH, specific gravity and urobilinogen
- Coagulation: PT (sec), PT (INR), aPTT

Clinical laboratory test results will be assigned a Low/Normal/High (L/N/H) classification according to whether the value is below (L), within (N), or above (H) the laboratory parameter's reference range. Shifts from baseline to each post-baseline visit will be provided for each laboratory parameter by treatment group.

Abnormal laboratory test results (i.e., results assigned as L/H) will be listed in a by-subject data listing.

CSF assessments, which include WBC, RBC, protein, and glucose, will be gathered locally. These measurements will subsequently be converted to standard units. The test results for WBC and protein will be descriptively summarized by visit and treatment group.

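### Safety laboratory samples are fasted at Baseline but need not be fasted afterwards, so within-arm glucose and lipid changes and shifts can reflect a meal

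*Protocol*

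**What the plan says.** The note to the clinical laboratory row of protocol Table 4 reads "Safety laboratory assessments at Baseline should be performed fasted. All other safety laboratory assessments are not required to be performed fasted". Section 8.1.8 repeats the rule for the later samples: "All other safety laboratory assessments are not required to be taken under fasted conditions". Because it appears in both places, the rule is deliberate and not a slip in the table.

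Table 4 places the Baseline draw in Days -22 to -1, shows no draw on Day 1, and then draws at Months 1, 2, 3, 6, 9 and 12.

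SAP Section 3.4.2 fixes the reference: "For safety endpoints, the baseline value is defined as the last non-missing assessment prior to the first study drug administration". SAP Section 6.2 sets two analyses against it: "The continuous test results and change from baseline will be descriptively summarized by visit and treatment group", and "Shifts from baseline to each post-baseline visit will be provided for each laboratory parameter by treatment group". The chemistry list in that section includes "gamma-glutamyl transpeptidase, glucose, high-density lipoprotein, low-density lipoprotein", then "total protein, triglycerides, urea, and uric acid", and also total cholesterol.

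Protocol Section 9.3.2 adds a further summary from the same follow-up samples: "On-study laboratory abnormalities including hematology and chemistry will be summarized using worst grade per NCI CTCAE criteria".

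**The concern.** The reference value is normally taken fasted, while the follow-up value may be fasted or fed. For analytes that respond to a meal, the difference between them mixes a change of fasting state with any change on treatment. SAP Section 6.2 neither separates the two nor carries a caveat, and neither document mentions recording fasting status. Dosing does not settle it, since Section 6.4 lets tablets be taken with or without food.

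The protocol itself treats fasting as relevant: it asks for it at Baseline, and exclusion criterion 16 gives inability to fast as an example of an excluding condition.

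Safety is a primary objective, and the laboratory tables are descriptive. At stake is whether a rise in glucose or triglycerides, or a count of normal-to-high shifts, in a dose column can be taken at face value. A modest metabolic effect of the drug could also be harder to see against a raised and more variable background.

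**Working it through.** **Step 1. Which samples are compared.** The last laboratory draw before first dose in Table 4 is the one in Days -22 to -1, so under SAP Section 3.4.2 it is the usual baseline and it is fasted. If it is missing, the baseline falls back to Screening, where fasting is not required. All six post-baseline draws fall under the not-required rule, though some may happen to be fasted. So most, but not all, comparisons set a fasted value against one of unknown state.

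**Step 2. Effect on the contrast with placebo.** Let *d* be the meal effect, *q* the share of follow-up samples that are fed, and *δ* the drug effect on the mean. Taking meal and drug effects as additive, and *q* as unrelated to treatment:

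- mean change on placebo = *qd*
- mean change on active = *δ* + *qd*
- difference = *δ*

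The meal term cancels between arms but stays in each arm's own mean change. With no drug effect, the expected shift rates are likewise equal across arms.

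**Step 3. Illustrative size.** The plan states no figure to reproduce. All inputs in this step are assumptions: the fasted analyte is standard normal, the upper limit of normal is *U* = 1.96 SD, the correlation *r* between baseline and follow-up is 0.5 to 0.7, *d* is 0.5 to 1.5 SD, and there is no drug effect. The probability of High at follow-up, given not High at baseline, is

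(1 − *q*)·s(0) + *q*·s(*d*), where s(*d*) = [Φ(*U*) − Φ₂(*U*, *U* − *d*; *r*)] / Φ(*U*).

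The SD of change, relative to having all samples fasted, is √{[2(1 − *r*) + *d*²*q*(1 − *q*)] / [2(1 − *r*)]}.

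Ranges below run over *r* = 0.5 to 0.7.

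| Meal effect | Shift to High, all fasted | Half of follow-up fed | All follow-up fed | Mean change, half fed | SD ratio, half fed |
|---|---|---|---|---|---|
| 0.5 SD | 1.7–2.1% | 3.8–4.3% | 5.9–6.5% | 0.25 SD | 1.03–1.05 |
| 1.0 SD | 1.7–2.1% | 8.5–8.9% | 15.2–15.8% | 0.50 SD | 1.12–1.19 |
| 1.5 SD | 1.7–2.1% | 16.2–16.6% | 30.7–31.1% | 0.75 SD | 1.25–1.39 |

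Example for the first row with *r* = 0.5: 0.5 × 2.1% + 0.5 × 6.5% = 4.3%. Example for the largest SD ratio (*r* = 0.7, *d* = 1.5): √[(0.6 + 2.25 × 0.25) / 0.6] = √1.94 = 1.39.

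**Step 4. In subjects.** The 144 subjects planned for Parts A, B, D and E, split 1:1 between dose levels and 2:1 within each, give 72 × 2/3 = 48 per dose and 2 × 24 = 48 on placebo. Per visit and analyte, about one subject in 48 would shift to High by chance with all samples fasted (48 × 0.021 = 1.0). With half the follow-up samples fed it would be about two to eight (48 × 0.038 = 1.8; 48 × 0.166 = 8.0), in each arm alike.

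**The case against.** The strongest reply is that the trial has a concurrent, blinded, randomized placebo group, that the primary safety objective is framed against placebo, and that SAP Section 6.2 tabulates by treatment group. Fasting rules are identical in all arms, so a reader who looks across the columns is not misled. This stands. One might infer from the mismatch that the drug-versus-placebo comparison of glucose or lipids is biased; Step 2 shows that it is not. Nor do the documents say that the tables are to be read one arm at a time. What remains is the within-arm change and shift counts, which the SAP does plan to report, and the added variance.

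A second reply concerns size. A reader might infer a very large effect. For example, assume fasted glucose of mean 5.1 and SD 0.5 mmol/L, fed glucose of mean 5.5 to 5.9 and SD 0.9 to 1.1, an upper limit of 6.1, and independent values. Then 25 to 42% of placebo subjects shift to High when every sample is fed, and 13 to 22% when half are. None of those inputs is in the documents, and the first range requires every subject to be fed, so it is not a finding about this trial. The illustration in Step 3 is no better anchored; it shows direction and plausible scale only.

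Third, the point is confined. Section 8.2.1 keeps laboratory abnormalities that need no intervention or further investigation out of adverse event reporting, so an isolated fed value should not by itself enter those tables. The primary efficacy endpoint is untouched. Finally, that fasting status goes unrecorded is an inference from silence: the case report form, laboratory manual and table shells are not part of these documents.

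**Conclusion.** The point holds for within-arm results. The plan normally compares a fasted baseline with follow-up samples of uncontrolled fasting state, and reports change and shifts for glucose, triglycerides, LDL, HDL and total cholesterol as if the two were alike. Those changes and normal-to-high shifts can come from a meal.

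It does not hold as a claim that every comparison is fasted-to-fed, because a missing Baseline sample falls back to Screening and some follow-up samples may be fasted. It does not hold as a claim of bias against placebo either: provided treatment does not alter how often subjects attend fed, the contrast is unbiased and only noisier, with an SD of change up to 1.39 times larger in the illustration.

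The true size cannot be derived from the documents. On the assumptions in Step 3, shifts to High rise from about 2% to roughly 4 to 17% per visit when half the follow-up samples are fed. The five analytes need not respond equally to a meal, and the documents give no figure for any of them. This is a worthwhile, inexpensive correction to the safety tables and does not threaten the trial's main conclusions.

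**What to change.** 1. Record fasted yes/no at each laboratory draw. For samples already taken, retrieve it from source documents or laboratory requisitions where it exists.
2. In SAP Section 6.2, present the change and shift tables for glucose, triglycerides, LDL, HDL and total cholesterol by that flag, with the fasted-to-fasted comparison shown separately and unknown status as its own category.
3. Footnote these tables to say that Baseline was fasted and later samples need not have been, and that interpretation should rest on the comparison with placebo.

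The cost is one data field, some SAP wording and smaller table cells. Status may be unrecoverable for many samples: the SAP is dated 17 March 2025, and its Section 3.3 reports that the subjects in the interim analysis had reached 12 months by June 2024. In that case the footnote is the part that can still be done in full.

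Using the Screening sample as the reference instead is not recommended. Not required to fast is an uncontrolled condition, not one matched to follow-up; Screening may be as early as Day -57; and the change would give up the one sample whose fasting state is specified.
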